# Statistical Analysis Plan

Study alias & e-track number(s): Flu CC-SUIV-AS03-001 (201598)

- *The distribution of antibody titers for anti-H3 stalk ELISA will be displayed using reverse cumulative distribution curves.*
- the scatter plot of ELISA antibody results to the H3 stalk with the microneutralizing antibody results to the H3 stalk at D0 and *at all timepoints* will be presented to examine the correlation in all the study cohort. One scatter plot will be developed for each study/product. Furthermore, the correlation between the level of ELISA antibody with the level of microneutralizing antibody to the H3 stalk, *at all vaccination timepoints* may be explored using a Deming regression. However, the results should be interpreted with cautious due to small sample size and testing result variations in H3 stalk ELISA and H3 stalk MN.

## 6.2.2. Between groups assessment

### 6.2.2.1. For adult H5N1, H9N2, and H1N1 study cohorts

- For each **Group 1-related** study and for anti-H1 stalk ELISA results for adult H5N1, H9N2 and H1N1 study cohort, if available:
  - The difference in percentage of subject with at least 4-fold increase at *all applicable timepoints (D21, D42, D182, and D385) for which data are available* compared to Day 0 (i.e. adjuvanted group minus non-adjuvanted group *within each study cohort*, and the asymptotic standardized 95% CI, will be computed for each study cohort, separately.
  - The adjusted GMT ratio (adjuvanted group to non-adjuvanted group *within each study cohort*) of anti-H1 stalk ELISA antibodies for adjuvanted vaccine over non-adjuvanted vaccine at all timepoints (D21, D42, D182, and D385) for which data are available and the two-sided 95% CI on each GMT ratio will be computed for each study cohort, separately. ANCOVA models on the logarithm10 transformation of the titers, including the vaccine group as fixed effect and age category (<30 years and >=30 years) and the anti-H1 stalk ELISA result at Day 0 as covariates.
- For H1N1 study cohort and for anti-N1 NA ELISA results, if available:
  - The difference in percentage of subject with at least 4-fold increase at all time points (D21, 42 and 182) compared to Day 0 (i.e. adjuvanted group minus non-adjuvanted group, and the asymptotic standardized 95% CI, will be computed.
  - The adjusted GMT ratio (adjuvanted group to non-adjuvanted group) of anti-N1 NA ELISA antibodies for adjuvanted vaccine over non-adjuvanted vaccine at all timepoints (D21, D42 and D182) for which data are available and the two-sided 95% CI on each GMT ratio will be computed. ANCOVA models on the logarithm10 transformation of the titers, including the vaccine group as fixed

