# Statistical Analysis Plan

Study alias & e-track number(s): Flu CC-SUIV-AS03-001 (201598)

*in the Table.*

§ Exact number of subjects per treatment uncertain, but likely to be in this range

\* From D0, D21, D42, and D182 time points (no D385)

\*\* From D0, D21, D42, and D385 time points (no D182)

- **Blinding:** Laboratory staff conducting the testing will have knowledge of the subject number, treatment received, and specimen time-point for every specimen tested
- **Randomization:** The primary studies were randomized and the archived serum samples from these studies that will be retrospectively analyzed in the current study will be subjected to a sub-randomization procedure prior to selection for inclusion in the serology analysis.

The target is to randomly select approximately 30 subjects from each of the 3 adult studies (***Q-Pan H1N1-019, CC-Pan H5N1-001, and Q-Pan H9N2-001***) who: 1) received the adjuvanted standard dose vaccine candidate, and 2) were in the ATP-I and Persistence cohort (depending on the study) of the completed studies, and 3) have valid vaccine homologous HI result available at all required timepoints where HI test is done and MN result available at Day 0 and 21 (for H5N1 and H9N2 studies only). Within each study cohort, after subjects are selected from the adjuvanted (AS) group, subjects who received the unadjuvanted standard dose vaccine candidate will be matched (1:1) by subject age (<30 years and  $\geq$  30 years) and study center to the selected subjects from the adjuvanted vaccine group. Such matched pairs will then be checked to confirm if they have a sample with adequate volume at every time point.

***Furthermore, subjects assigned to the CMI and MN subset in study H9N2 and subject with available homologous MN result in the CC-H5N1-001 study should be preferentially selected from adjuvant group.*** In order to select 3 independent study cohorts of approximately 60 subjects each, allocated 1:1 to an adjuvanted or unadjuvanted formulation, ~40 subjects from the AS group who meet the above criteria in each study (note that criterion #3 for MN result is for the H5N1 and H9N2 studies only), will be randomly selected. However, if fewer than 40 subjects meet the above selection criteria, then all the available subjects will be selected.

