# Statistical Analysis Plan

Study alias & e-track number(s): Flu CC-SUIV-AS03-001 (201598)

*For the adult Q-Pan-005 study, all evaluable serum specimens (in the ATP cohort for immunogenicity) from Day 0, 42, 182, 224, 549, 591 and 729 of the 18 to 40 years of age subjects enrolled in group C and G in the Q-Pan-005 (110624) study and for the H5N1-012 study, all evaluable serum samples (in the ATP cohort for immunogenicity) from Day 0, 21, M6, M12, M12+21 days and M18 of the subjects enrolled in the VT/VT/12M and the VT/IN/12M groups will be used (i.e. no random selection for the sub-cohort).*

*For the adult FLU D-QIV-015 study, approximately 30 samples (in the ATP cohort for immunogenicity) pre-vaccination (Day 0) and post-vaccination (Day 21) from subjects 18-≤ 39 years who received D-QIV-IP, will be assessed. D-QIV-IP is the IIV4 manufactured in Dresden (FLU D-QIV) with an optimized manufacturing process. FLU D-QIV IP has demonstrated to be non-inferior in terms of immunogenicity to FLU-QIV manufactured with the previously licensed manufacturing process.*

*For exploratory analysis of samples from the adult Q-Pan-H7N9 study: approximately 30 subjects having received the adjuvanted standard H7N9 candidate vaccine dose and approximately 30 subjects having received the unadjuvanted standard candidate vaccine dose will be randomly selected to generate the serology sub-cohort in which both groups will match in terms of age and center. First, the subjects from the adjuvanted group will be selected. These subjects will have had to be included in the ATP-I and persistency cohorts of the primary study and have homologous HI results available for most of the applicable timepoints. Preference will be given to subjects who also have available results for homologous MN. Once these subjects are selected, the non-adjuvanted group will be selected to match the adjuvanted group by age (<30 years and ≥ 30 years) and by center. In order to select the study cohort, allocated 1:1 to the adjuvanted or the unadjuvanted group ~ 40 subjects from the AS group who meet the above criteria will be selected.*

*Please note that analysis to be performed and table to be presented for the exploratory mice experiment will be presented separately as it will be done by pre-clinical statistical team.*

The following group names and description will be used for the statistical analyses:

Group order in tables	Group label in tables	Group definition for footnote

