## 6.2.2.2. For H7N9 study only

*For H7N9 study and for anti-H3 stalk ELISA results, if available:*

- The difference in percentage of subject with at least 4-fold increase at all applicable timepoints (D21, D42, D182, and D385) for which data are available compared to Day 0 (i.e. adjuvanted group minus non-adjuvanted group, and the asymptotic standardized 95% CI, will be computed for each study cohort, separately.*
- The adjusted GMT ratio (adjuvanted group to non-adjuvanted group) of anti-H3 stalk ELISA antibodies for adjuvanted vaccine over non-adjuvanted vaccine at all timepoints (D21, D42, D182, and D385) for which data are available and the two-sided 95% CI on each GMT ratio will be computed. ANCOVA models on the logarithm10 transformation of the titers, including the vaccine group as fixed effect and the anti-H3 stalk ELISA result at Day 0 as covariates.*

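### The between-group analyses leave out factors used to match the groups: centre in every ANCOVA, age category in the H7N9 ANCOVA, and both in the responder-difference interval

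*SAP*

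**What the plan says.** **Selection.** SAP Section 2 (Randomization) first draws the adjuvanted subjects. For the H1N1, H5N1 and H9N2 adult studies, "subjects who received the unadjuvanted standard dose vaccine candidate will be matched (1:1) by subject age", in the two bands under 30 and 30 or over, and by "study center to the selected subjects from the adjuvanted vaccine group". It then adds: "Such matched pairs will then be checked to confirm if they have a sample with adequate volume at every time point". For H7N9 the same two factors apply: "the non-adjuvanted group will be selected to match the adjuvanted group by age (<30 years and ≥ 30 years) and by center".

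**Analysis.**
- Section 6.2.2.1, anti-H1 stalk: ANCOVA on log10 titres with vaccine group, "age category (<30 years and >=30 years) and the anti-H1 stalk ELISA result at Day 0 as covariates". There is no centre, stratum or pair term.
- Section 6.2.2.1, anti-N1 NA (H1N1 cohort): the same form, with the anti-N1 Day 0 result.
- Section 6.2.2.2, anti-H3 stalk (H7N9 cohort): ANCOVA on log10 titres "including the vaccine group as fixed effect and the anti-H3 stalk ELISA result at Day 0 as covariates". Age category is absent as well as centre.
- Both sections: the difference in the percentage with at least a four-fold rise gets an asymptotic standardized 95% interval. No stratification or pairing is mentioned.

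The SAP gives no reason for leaving out centre or for the shorter H7N9 model.

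**The concern.** Four cohorts are selected by one rule and then analysed by two different models, and neither model carries every factor used in the selection. Matching on a factor makes the groups alike on it, so the variance of the group difference falls by whatever that factor explains. A standard error from a model without the factor does not register this fall, and the interval comes out wider than the design requires.

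Table 1 expects 20–30 subjects per group, so precision is scarce. Section 6.2.2 is the only between-group assessment in the SAP. It serves the adjuvant-effect objective in Section 3.2 and its tertiary counterparts in Section 3.3. The H7N9 omission of age is the harder to explain: that study enrolled ages 18–64, the selection bands are the same, and the SAP treats age as relevant both in the sister models and in its age-stratified analysis of H5N1-012.

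**Working it through.** The SAP states no power or precision figure for these comparisons, so there is none to reproduce. The omissions are shown by setting the sections side by side:

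| Analysis | Matched on | Age category used | Centre used |
|---|---|---|---|
| Anti-H1 stalk ANCOVA (H1N1, H5N1, H9N2) | age category, centre | yes | no |
| Anti-N1 NA ANCOVA (H1N1) | age category, centre | yes | no |
| Anti-H3 stalk ANCOVA (H7N9) | age category, centre | no | no |
| Four-fold responder difference (all four cohorts) | age category, centre | not stated | not stated |

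**Inputs for the size.** From the SAP: 20–30 per group (Table 1), two-sided 95% intervals (Section 7.1). Assumed, because the SAP gives none: the share of residual variance due to centre and age, the number of centres, the titre SD and the responder rates.

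**1. Analytic.** If omitted, balanced matching factors explain a share r of the residual variance, the interval is too wide by 1/√(1−r), and coverage is 2Φ(1.96/√(1−r)) − 1.

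| r (assumed) | Width ratio | Coverage |
|---|---|---|
| 0 | 1.00 | 95.0% |
| 5% | 1.03 | 95.6% |
| 10% | 1.05 | 96.1% |
| 20% | 1.12 | 97.2% |
| 30% | 1.20 | 98.1% |

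For example, r = 0.20 gives 1/√0.80 = 1.118.

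**2. Simulation.** ANCOVA on log10 titres, pairs matched on age category and centre, 5 centres, SD 0.4 log10, true difference 0.30 log10, 3000 runs per scenario. The Monte Carlo error on coverage is √(0.95 × 0.05/3000) ≈ 0.4 points. Cells show coverage and mean interval width in log10.

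| n per group | Centre / age share | Age, no centre (as 6.2.2.1) | Neither (as 6.2.2.2) | Age and centre |
|---|---|---|---|---|
| 30 | 0 / 0 | 95.1%, 0.415 | 95.1%, 0.415 | 94.9%, 0.416 |
| 30 | 10% / 10% | 95.3%, 0.389 | 96.2%, 0.411 | 94.3%, 0.372 |
| 30 | 20% / 10% | 97.0%, 0.383 | 97.7%, 0.406 | 95.1%, 0.348 |
| 30 | 30% / 10% | 97.4%, 0.376 | 98.3%, 0.399 | 95.0%, 0.322 |
| 20 | 20% / 10% | 96.7%, 0.477 | 97.5%, 0.505 | 94.9%, 0.435 |

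In the 20% / 10% case with 30 per group, the planned intervals are 0.383/0.348 = 1.10 and 0.406/0.348 = 1.17 times as wide as the interval from the model with both factors. The mean estimate stayed between 0.298 and 0.303 at 30 per group, so no bias appeared. Section 7.1 drops subjects with missing results, which can break the balance. With 10% missing at random in the same case, coverage was 96.2%, 97.3% and 95.0%.

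**3. Responder difference.** Assume 60% against 30% with 30 per group. The unpaired half-width is 1.96 × √[(0.24 + 0.21)/30] = 0.240. With within-pair correlation ρ, the variance is [0.45 − 2ρ√(0.24 × 0.21)]/30. The half-width is then 0.228, 0.215 and 0.201 at ρ = 0.1, 0.2 and 0.3, and the unpaired interval covers 96.1%, 97.2% and 98.1%.

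**The case against.** The case for leaving the plan alone has real weight.

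- **The error is on the safe side.** Leaving out a balanced factor gives over-coverage and no bias in the GMT ratio. This stands. A reader might infer that the intervals are invalid or the estimates confounded; neither the design nor the calculations support that.
- **The size is assumed.** The SAP gives no variance shares, titre SD or number of centres. Section 2 assigns the ELISAs to one laboratory, so differences between testing laboratories are not an obvious source of a centre effect. This stands: the loss may be nil.
- **The rank is modest.** The anti-H1 comparison is secondary, and the anti-N1 and H7N9 comparisons are tertiary. The co-primary endpoints are within-group and unaffected, and Section 6 makes every analysis descriptive. This stands: no error rate or decision rule is at risk.
- **The matching is coarse.** It uses two age bands by centre, and pairs are named only for the check of sample volume. This argues against insisting on a paired analysis, but not against using the strata.

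Two stronger readings are tempting. One is that the Day 0 titre enters untransformed. Section 6.2.2 refers to a log10 transformation of the titres and then to the Day 0 result, which can as well be read as covering baseline, so this is unclear wording and not a stated error. The other is that age should enter in years. The models in Section 6.2.2.1 use exactly the bands used for matching, so on age they do follow the design; continuous age would be a preference beyond it.

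**Conclusion.** The point holds as one of consistency and precision. Centre is omitted from all three ANCOVAs, age category is omitted from the H7N9 ANCOVA although it was used to select that cohort, and the responder-difference interval states no stratification. These facts need no assumption.

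The consequence is conservative intervals: about 5–20% too wide, with coverage of about 96–98%, if the omitted factors explain 10–30% of residual variance. Those shares are assumptions, and at zero there is no loss. The calculations do not support any claim of bias or under-coverage. The change is worth making because it is cheap and uses only factors the plan already relies on for selection.

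**What to change.** In SAP Section 6.2.2:

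1. Add age category (under 30, 30 or over) to the H7N9 anti-H3 stalk ANCOVA, so that it agrees with the other matched cohorts.
2. Add study centre to the anti-H1 stalk, anti-N1 NA and anti-H3 stalk ANCOVAs, with a rule for pooling small centres fixed before results are seen.
3. Compute the interval for the difference in four-fold responders as a score (Miettinen–Nurminen) interval stratified by age category and pooled centre.
4. While editing, write the baseline covariate as the log10 Day 0 titre, to settle the wording.

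If the sponsor prefers the present models, the SAP should say why centre is left out and why H7N9 differs.

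The cost is a few degrees of freedom, and sparse strata if centres are not pooled. In the simulation with five centres and no centre or age effect, including both factors changed the mean width only from 0.415 to 0.416 log10 at 30 per group, and from 0.515 to 0.518 at 20 per group. No new data are needed.

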# Statistical Analysis Plan

Study alias & e-track number(s): Flu CC-SUIV-AS03-001 (201598)

effect and age category (<30 years and >=30 years) and the anti-N1 NA ELISA result at Day 0 as covariates.

## 6.2.2.2. For H7N9 study only

*For H7N9 study and for anti-H3 stalk ELISA results, if available:*

- The difference in percentage of subject with at least 4-fold increase at all applicable timepoints (D21, D42, D182, and D385) for which data are available compared to Day 0 (i.e. adjuvanted group minus non-adjuvanted group, and the asymptotic standardized 95% CI, will be computed for each study cohort, separately.*
- The adjusted GMT ratio (adjuvanted group to non-adjuvanted group) of anti-H3 stalk ELISA antibodies for adjuvanted vaccine over non-adjuvanted vaccine at all timepoints (D21, D42, D182, and D385) for which data are available and the two-sided 95% CI on each GMT ratio will be computed. ANCOVA models on the logarithm10 transformation of the titers, including the vaccine group as fixed effect and the anti-H3 stalk ELISA result at Day 0 as covariates.*

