- MGI with 95% CI will be tabulated for anti-H3 stalk ELISA, anti-H3 stalk MN, anti-H4 HA full length ELISA, anti-H10 HA full length ELISA and vaccine heterologous MN*
- Percentage of subjects with at least 4-fold increase from Day 0 to Day 42 for anti-H3 stalk ELISA, anti-H1 stalk MN, anti-H4 full length HA ELISA, anti-H10 full length HA ELISA and vaccine heterologous MN, with exact 95% CI, will be calculated.*

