# Statistical Analysis Plan

Study alias & e-track number(s): Flu CC-SUIV-AS03-001 (201598)

of the assay will be given an arbitrary value of half the cut-off for the purpose of GMT calculation.

- The 95% CI for geometric mean titres (GMTs) will be obtained within each group separately. The 95% CI for the mean of log-transformed titre will be first obtained assuming that log-transformed values were normally distributed with unknown variance. The 95% CI for the GMTs will be then obtained by exponential-transformation of the 95% CI for the mean of log-transformed titre.
- Four-fold antibody titer increase is defined as post/pre for seropositive subjects; and post/half of the cut off value for seronegative subjects
- *Ten-fold antibody titer increase is defined as post/pre for seropositive subjects; and post/half of the cut off value for seronegative subjects*
- All CI computed will be two-sided 95% CI. The exact 95% CIs for a proportion within a group will be based on the method by Clopper [Clopper, 1934\*].

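### The H7N9 ANCOVA omits the age category on which the groups are matched, and the H7N9 fold-rise method in SAP 6.2.1 disagrees with the endpoints in 4.3

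*SAP*

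**What the plan says.** **Selection.** SAP section 2 selects the adjuvanted H7N9 subjects first. Then "the non-adjuvanted group will be selected to match the adjuvanted group by age (<30 years and ≥ 30 years) and by center". The target is about 30 per group (20-30 in Table 1), and the age range is 18-64 years. The adult H1N1, H5N1 and H9N2 cohorts are matched on the same age split and on center.

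**Models.** For the anti-H1 stalk GMT ratio in those three cohorts, 6.2.2.1 gives an ANCOVA on log10 titre with "vaccine group as fixed effect and age category (<30 years and >=30 years) and the anti-H1 stalk ELISA result at Day 0 as covariates". The anti-N1 model for the H1N1 cohort has the same structure. For H7N9, 6.2.2.2 gives "including the vaccine group as fixed effect and the anti-H3 stalk ELISA result at Day 0 as covariates", with no age term. No reason is stated, and section 9 reports no changes.

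**Fold rises.** The H7N9 part of 6.2.1 has one fold-rise bullet. It is limited to the 4-fold rise at Day 42, and its assay list begins "for anti-H3 stalk ELISA, anti-H1 stalk MN, anti-H4 full length HA ELISA". Section 4.3 plans 4-fold and 10-fold rises for anti-H3 stalk ELISA and anti-H3 stalk MN (Days 21 and 42), for anti-H4 and anti-H10 (Day 42 and Month 12) and for heterosubtypic MN (Day 42).

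**The concern.** There are two separate matters.

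The first is the model. A design that balances a factor by matching gains precision from it only if the analysis also removes that factor's variation from the residual. The SAP does so for three matched adult cohorts and not for the fourth, which has as wide an age range as H9N2 and a wider one than H1N1 (19-40). Section 2 also stratifies the H5N1-012 cohort by age to look for an age effect, so the authors consider age potentially relevant. Matching may also not survive into the analysed data. Section 7.1 excludes missing or non-evaluable results. For the other three cohorts section 2 checks each matched pair for adequate sample volume at every time point, but it states no such check for H7N9.

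The second is the conflict between 6.2.1 and 4.3. Whoever programs the H7N9 tables finds one assay and set of timepoints in the methods and another in the endpoints, and must choose.

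**Working it through.** The SAP gives no precision or sample-size figure for H7N9, so there is none to reproduce.

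**1. Precision cost of omitting age**

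Inputs from the SAP: n = 20 or 30 per group, 1:1; two-sided 95% CI; model terms as above. Assumption: the partial R2 of age category given group and Day 0 titre, varied from 0 to 0.30, because the SAP gives no value.

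With age balanced between groups and N = 2n, the ratio of CI half-widths on the log10 GMT ratio (age omitted over age included) is

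[t(0.975, N-3) / t(0.975, N-4)] / sqrt(1 - R2).

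The degrees of freedom are 57 and 56 at n = 30, and 37 and 36 at n = 20.

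| Assumed partial R2 | n = 30 | n = 20 |
|---|---|---|
| 0 | 0.9996 | 0.9991 |
| 0.05 | 1.026 | 1.025 |
| 0.10 | 1.054 | 1.053 |
| 0.20 | 1.118 | 1.117 |
| 0.30 | 1.195 | 1.194 |

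The extra degree of freedom pays for itself once R2 exceeds about 0.001 (n = 30) or 0.002 (n = 20).

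On the titre scale, assume a residual log10 SD of 0.4 without the age term and n = 30. The CI multiplies or divides the GMT ratio by 10^(t × 0.4 × sqrt(2/30)) = 1.61. With age in the model the factor is 1.57 at R2 = 0.10 and 1.53 at R2 = 0.20.

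**2. Simulation check**

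4000 trials, 30 per group, 30% of each group in one age stratum, age effect 0.4 log10, residual SD 0.4 (all assumed). The age variance is 0.4² × 0.3 × 0.7 = 0.0336, so the expected width ratio is about sqrt(0.16 + 0.0336)/0.4 = 1.10. The simulated ratio was 1.103. Coverage was 96.9% without age and 94.6% with it. Omitting a balanced, prognostic factor therefore makes the interval conservative, not invalid.

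**3. Fold-rise percentages: 4.3 against the H7N9 bullet in 6.2.1**

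| Assay | Planned in 4.3 (4-fold and 10-fold each) | In the 6.2.1 bullet |
|---|---|---|
| Anti-H3 stalk ELISA | D21, D42 (4 items) | 4-fold D42 |
| Anti-H3 stalk MN | D21, D42 (4 items) | 4-fold D42, under the name anti-H1 stalk MN |
| Anti-H4 | D42, Month 12 (4 items) | 4-fold D42 |
| Anti-H10 | D42, Month 12 (4 items) | 4-fold D42 |
| Heterosubtypic MN | D42 (2 items) | 4-fold D42 |

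Section 4.3 therefore lists 4 + 4 + 4 + 4 + 2 = 18 assay-by-timepoint percentages. The bullet states 4 correctly and 1 under the wrong assay. It is silent on 13: all 9 of the 10-fold items and 4 of the 4-fold items (D21 for ELISA and for MN, Month 12 for H4 and for H10). One of the 13, the 4-fold rise at D21 for anti-H3 stalk ELISA, is needed anyway for the between-group difference in 6.2.2.2. The corresponding Group 1 text in 6.2.1 has a 10-fold bullet and refers to the endpoints for timepoints.

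**The case against.** **The model is valid as written.** An ANCOVA on group and baseline titre is legitimate. A reader might infer that omitting a matching factor biases the H7N9 GMT ratio. The SAP does not support that: with age balanced, the estimate is unaffected and the interval is at worst conservative. Nor is the loss of precision certain, since it needs an age effect that the SAP does not quantify. This objection stands and sets the size of the point.

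**The SAP has no rule that matching factors are modelled.** Center is matched on too and is in none of the ANCOVAs. This also stands. The case rests on the unexplained difference from 6.2.2.1 and on the negligible cost of the term, not on a general principle.

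**The endpoints are not dropped.** A reader might infer from 6.2.1 that the 10-fold and Day 21 results have no method, or that the neutralization readout of this cohort is lost. Neither follows. Section 4.3 requires these percentages with 95% CIs, and 7.1 defines 4-fold and 10-fold increases and sets exact intervals for proportions. The lead-in and the seropositivity, GMT and MGI bullets of the same H7N9 list all say anti-H3 stalk MN, and no H7N9 endpoint calls for anti-H1 stalk MN. What remains is a slip in one assay name and a bullet narrower than the endpoints it serves.

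**Conclusion.** The point holds at low severity. The H7N9 ANCOVA omits, without a stated reason, the age category that is both a matching factor and a covariate in the comparable models. If age is prognostic after baseline adjustment, the CI for the GMT ratio is about 2.6% wider than needed at a partial R2 of 0.05, 5% at 0.10 and 12% at 0.20 (log scale, 30 per group). If age is not prognostic, nothing is lost. These R2 values are assumptions. There is no bias while the matching holds. If matched partners have missing results, the model leaves any resulting age imbalance uncorrected; that effect is not quantified here.

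The contradiction between 6.2.1 and 4.3 needs no assumption: one assay is misnamed and 13 of 18 planned percentages are not in the bullet. The consequence is ambiguity for the programmer. The analyses are tertiary, exploratory and descriptive, with no test or decision attached.

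**What to change.** 1. In 6.2.2.2, add age category (<30, >=30 years) as a covariate in the H7N9 ANCOVA, as in 6.2.2.1.
2. In the H7N9 fold-rise bullet of 6.2.1, replace anti-H1 stalk MN with anti-H3 stalk MN.
3. Align that bullet with 4.3: 4-fold and 10-fold percentages at Days 21 and 42 for anti-H3 stalk ELISA and MN, at Day 42 and Month 12 for anti-H4 and anti-H10, and at Day 42 for heterosubtypic MN.

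The cost is SAP wording and one degree of freedom in one model. No new data are needed, since age is already used for the matching. The change is best made before the H7N9 results are analysed.
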